**Table. Determination of the Modified MASI (mMASI) Score**

Location of Melasma	Scoring a	Calculation for Total Score b
Forehead	(0.3) (A) (D)	
Left malar	(0.3) (A) (D)	Forehead mMASI Score + Left Malar mMASI Score + Right Malar mMASI Score + Chin mMASI Score = Total mMASI Score
Right malar	(0.3) (A) (D)	
Chin	(0.1) (A) (D)	

Abbreviation: MASI, Melasma Area and Severity Index.

a Scoring system: A, Area of involvement rated 0 to 6: 0 indicates absent; 1, <10%; 2, 10% to 29%; 3, 30% to 49%; 4, 50% to 69%; 5, 70% to 89%; 6, 90% to 100%. D, Darkness rated 0 to 4: 0 indicates absent; 1, slight; 2, mild; 3, marked; 4, severe.

b Total mMASI score range is 0 to 24 and calculated by adding scores for 4 areas of the face.

Safety Endpoints:

- Incidence of adverse safety events during the treatment and follow up period
- Subject assessment of pain and discomfort associated with treatments using an 11-point visual assessment scale (VAS) pain score

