### Procedure:

#### Visit 1 (Screening and Initial Treatment Visit)

- Verify that subject is qualified to participate in the study.
- Ask subject to give personal information, such as name, date of birth, race and ethnicity.
- Review medical and dermatology (skin) history, including history of previous treatments to area being treated.
- Review past and current medications and skin care products.
- See how tall subject is and how much subject weighs
- If subject is a woman and can have children, urine will be tested to see if subject is pregnant. The study doctor or study staff will tell subject if pregnancy test results are positive. The results of the pregnancy testing must be negative in order for subject to be in the study.
- Supply patient with topical cysteamine cream and review instructions for its use
- Identify and examine the area (i.e, side) of face to which the Diode 1927 nm laser will be used (mapping)
- Take photos of face
- Perform grading of melasma
- Perform treatment according to guidelines stated in protocol
- Schedule the next study visit

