#### Visit 4 (Week 12)

- Assess side-effects of treatment
- See how tall subject is and how much subject weighs
- Take photos of face
- Perform grading of melasma
- Post-treatment questionnaire
- Evaluation of photos comparing visit 1 and 4 to be performed

**Risks and Discomforts:** Blistering, edema, erythema and local pain are typical reactions to laser treatment. A lesser possibility exists for hyperpigmentation, hypopigmentation scarring, and/or infection. These conditions may or may not resolve over time. As with any method of tissue destruction, there is a risk of infection and of scarring, which is minimized with proper wound care. Eye injury due to the use of the laser is a risk to the subject as well as the operator. The subjects may experience partial or permanent hair reduction. Risks of the topical include temporary irritation, burning or heating up sensation that resolves within 30 minutes

**Benefits:** The subjects may or may not show improvement of melasma on the treatment sites. There is no guarantee of success.

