The primary objective of our study is to determine the efficacy of combined topical cysteamine cream with a 1927 diode non-ablative laser (Clear + Brilliant Permea®; Solta Medical, Inc.), compared to topical cysteamine alone in the treatment of melasma. This efficacy will be assessed using modified Melasma Area and Severity Index (mMASI) scores, a validated physician assessment tool, at baseline and at follow up visits at week 4, 8 and 12 as well as Investigator Global Assessments. Secondary objectives also include an assessment of patient satisfaction which will be evaluated via patient questionnaires distributed to patients at baseline and at week 12. In addition, impact on quality of life will also be assessed utilizing the melasma quality of life scale (MELASQoL) questionnaire which will be administered to patients at baseline and at week 12.

Multiple studies have demonstrated the efficacy of topical cysteamine in the treatment of melasma. Mansouri et al. conducted a double-blind, randomized, controlled clinical study, which included 50 melasma patients, and demonstrated significant efficacy of topical cysteamine in the treatment of melasma. One comparative trial demonstrated that topical 5% cysteamine, though safe and well-tolerated, was less effective than topical 4% hydroquinone in the treatment of facial melasma; however, a later published response indicated that the concentration of cysteamine may have been less than the reported 5%. A single-blind, randomized comparative trial of 54 melasma patients found no statistically significant difference in the efficacy of topical cysteamine compared to topical tranexamic acid; however, cysteamine was better tolerated amongst the patients. Finally, Karrabi et al. also found that cysteamine 5% cream showed greater efficacy than the gold standard, modified Kligman's formula, in their randomized, double-blind trial of 50 patients with epidermal melasma.

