#### Sample Size Calculation:

A sample size is calculated to test the null hypothesis with a one-sided paired t-test for simplicity, although the final analysis may employ a statistically more powerful model.

We calculate that for a two-sided alpha level of 5%, a sample size of 20 subjects will enable us to test the null hypothesis with 80% power. In order to enable the analysis and take into account the potential for dropout we may include up to 25 patients.

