**Criteria of Evaluation (Study Endpoints):**

In person assessment by treating physician and photographic assessment in which blinded dermatologists compared photographs of the individual's face areas at baseline and visit 4 from all patients in the study.

Clinical Endpoints:

- In person assessment by treating physicians will measure change in mMASI of the subjects face at between baseline (visit 1) and week 4.
- The Global Aesthetic Improvement Scale (GAIS), a 5-point scale rating global aesthetic improvement in appearance, compared to pretreatment, as judged by the investigator and the subject will also be assessed. The rating categories used on this scale will be “worse” “no change” “improved” “much improved” and “very much improved”. The percent ranking improvements in the Investigator and Subject GAIS scale from baseline (visit 1) to visit 4 will be compared.
- Photographic assessment by two blinded dermatologists will measure changes will assess improvement in melasma by mMASI score. In addition, an investigator quartile improvement score from baseline to week 12 (0 – 0%, no improvement; 76%-100% - very significant improvement) will be assessed.

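### Sides of the face are randomised and compared, but no laser-side versus control-side difference in mMASI is named as an endpoint

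*Protocol*

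**What the plan says.** **The question is between sides.** Under Study population, all subjects receive cysteamine and one side of the face is chosen at random for laser. At Visit 1 staff are to "Identify and examine the area (i.e, side) of face to which the Diode 1927 nm laser will be used". The primary objective, under Background, is the efficacy of the combination "compared to topical cysteamine alone in the treatment of melasma", assessed by mMASI. Hypothesis 1 expects both sides to improve, and the combined side to improve more, on mMASI at weeks 4, 8 and 12.

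**The sections that define the analysis do not repeat it.**

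- Clinical Endpoints: the in-person assessment will "measure change in mMASI of the subjects face" from baseline. The photographic endpoint is improvement by mMASI score. Neither names a side.
- mMASI table: the one summary is "Forehead mMASI Score + Left Malar mMASI Score + Right Malar mMASI Score + Chin mMASI Score = Total mMASI Score", with the note "Total mMASI score range is 0 to 24 and calculated by adding scores for 4 areas of the face". Malar scores are split left and right; forehead and chin are not.
- Study Design: the label is before-after.
- Statistical Hypothesis: the null is that laser plus cysteamine brings no significant improvement. It has no comparator.
- Sample Size Calculation: the null is to be tested "with a one-sided paired t-test for simplicity, although the final analysis may employ a statistically more powerful model". The members of the pair are not given.
- Visit 4: "Evaluation of photos comparing visit 1 and 4 to be performed", which is a comparison over time.

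**The concern.** Cysteamine is applied to both sides, so the laser's contribution shows only in the difference between sides. A whole-face score adds the two sides, and its change over time contains the cysteamine effect twice and the added laser effect once. Followed as written, the plan could report improvement that cysteamine alone produced, in a trial whose purpose is to find out whether laser adds anything. If the paired test is meant as laser side against control side, the protocol does not say which score enters it, and the total cannot, because each subject has only one.

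**Working it through.** **Inputs**, all from the mMASI table: area A from 0 to 6, darkness D from 0 to 4, weights 0.3 (forehead), 0.3 (left malar), 0.3 (right malar) and 0.1 (chin).

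**1. The plan's own range.** Maximum A × D = 6 × 4 = 24. Total = 24 × (0.3 + 0.3 + 0.3 + 0.1) = 24. The stated 0 to 24 reproduces.

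**2. How much of the score belongs to a side.**

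- One malar row: 0.3 × 24 = 7.2. Two rows: 14.4, and 14.4/24 = 60%.
- Forehead plus chin: (0.3 + 0.1) × 24 = 9.6, and 9.6/24 = 40%. Each has one rating, so neither can be assigned to the laser or the control side.

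**3. The total does not identify the laser effect.** Take illustrative ratings with both malar rows at A = 4, D = 3, that is 0.3 × 4 × 3 = 3.6 each, and leave forehead and chin unchanged.

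| | Laser side after | Control side after | Fall, laser side | Fall, control side | Fall in total | Side difference in fall |
|---|---|---|---|---|---|---|
| Case 1 | 0.3 × 3 × 2 = 1.8 | 0.3 × 3 × 2 = 1.8 | 1.8 | 1.8 | 3.6 | 0 |
| Case 2 | 0.3 × 3 × 1 = 0.9 | 0.3 × 3 × 3 = 2.7 | 2.7 | 0.9 | 3.6 | 1.8 |

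The change in the total is the same with no laser effect and with a clear one. The malar rows separate the two cases.

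**4. A half-face score is a different instrument, not a split of the total.** Weights of 0.15 (half-forehead), 0.3 (malar) and 0.05 (half-chin) give 24 × 0.5 = 12 per side. Because area is banded, the halves need not add up to the whole. At D = 3, let the laser half of the forehead go from 60% (A = 4) to 5% (A = 1) while the control half stays at 60%. The half-scores fall by 0.15 × 3 × 3 = 1.35. With equal halves, the single forehead row goes from 60% (A = 4) to 32.5% (A = 3) and falls by 0.3 × 1 × 3 = 0.9.

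**5. Timing.** Clinical Endpoints puts the in-person mMASI change at week 4. The visit list schedules melasma grading at Visit 1 and Visit 4 (week 12) only. Background and hypothesis 1 place mMASI at weeks 4, 8 and 12. A side-difference endpoint needs one visit, and these sections do not agree on it.

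**The case against.** **The intent is documented.** Hypothesis 1 gives the contrast, the variable and the times, and the primary objective makes the same comparison. This stands: the protocol does state the side comparison. It states it as an objective and a hypothesis, while the endpoint list, null and design label describe something else.

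**The total is not named as the tested variable.** A reader might infer that the protocol commits to testing the whole-face total before against after. The documents do not go that far. Clinical Endpoints says mMASI, the table scores the malar regions separately, and the sentence introducing the endpoints speaks of areas of the face, a word that the Visit 1 list equates with side. The table also uses that word for regions, so the meaning is open. Any error rate calculated for a before-after test of the total would describe a test the protocol does not state, so none is given here.

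**A statistical analysis plan could settle it.** One may exist, and it could fix the score and the pairing before analysis. It therefore does not follow that any side comparison would be chosen after seeing the data. Such a plan still could not supply in-person half-forehead and half-chin ratings that were never taken, and it should not have to overrule the protocol's endpoint, null and design label.

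**Much is recoverable.** Malar ratings by side exist in both modes. The Photographs section provides standardised left, right and front views that could be re-rated by half. This stands; only the in-person half ratings would be lost.

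**A before-after endpoint has a use.** Objective A asks about improvement after three treatments, without a control. The whole-face total serves that objective.

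**Global ratings.** Background also lists "as well as Investigator Global Assessments", and a reader might infer that the investigator GAIS and quartile score must be given per side. The protocol does not equate those scales with that term, so the point is not made.

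**Conclusion.** The concern holds: this is a contradiction within the protocol, not a detail left for later. The randomised comparison is between sides, yet the endpoint list names no side difference, the only summary score adds the sides together, the design label and null have no control side, and the pairing is unstated. A change in the whole-face total cannot answer the primary objective: the same fall of 3.6 goes with a side difference of 0 or 1.8. That result follows from the table's weights alone; the ratings are illustrative, and no assumption about effect size or SD is needed. The malar rows, 60% of the score, can carry the comparison once they are named. The remaining 40% cannot be split by side as rated. The finding does not say that the side comparison is absent from the protocol or that the data could not support one.

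**What to change.** - **Clinical Endpoints:** make the within-patient difference (laser side minus control side) in mMASI change from baseline the efficacy endpoint, at one stated visit. First reconcile the week 4 given there with Visit 4 (week 12) in the visit list and with weeks 4, 8 and 12 in Background and hypothesis 1.
- **Score:** use the left and right malar rows already in the table as the default. A half-face score (0.15, 0.3, 0.05; 0 to 12 per side) can be a prespecified sensitivity analysis.
- **Sample Size Calculation:** state that the pair is laser side with control side.
- **Statistical Hypothesis and Study Design:** restate the null and the label as a between-side comparison.
- **Whole-face total:** keep it before-after, as descriptive for objective A.

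**Cost.** The malar score needs no new ratings if the stated visit is one at which grading is already scheduled, but it ignores 40% of the weight. The optional half-face score adapts the whole-face instrument that Background describes as validated. It raises the regions rated from 4 to 6 per grading. With up to 25 patients, that is at most 2 × 2 × 25 = 100 extra in-person ratings if grading is at visits 1 and 4, or 2 × 4 × 25 = 200 if at weeks 0, 4, 8 and 12. Two photographic readers add 2 × 2 × 25 × 2 = 200. These counts assume that the half ratings replace the undivided forehead and chin ratings. If those are kept so that the total stays exact, 4 ratings are added per grading instead of 2 and each count doubles. No new visit or imaging is needed.

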**Subject Risks:**

Risks to the subjects who participate in this study are the same as those subjects undergoing any dermatological laser treatment, such as for the removal of pigmented or vascular lesions, and permanent hair reduction to the upper lip area. Eye injury, due to the use of the laser, is a risk to the subject and the operator. Blistering, edema, erythema, and mild to moderate local pain are typical reactions to topical laser treatments. A lesser possibility exists for hyperpigmentation, hypopigmentation scarring, and/or infection. These conditions may or may not resolve over time.

**Risk Management:**

Subjects will be followed closely during the course of the trial and will have access to the investigators at all times via provision of after-hours telephone and/or pager numbers.

Any investigators, subjects or others present in the room while the laser treatment is rendered will wear suitable eye protection. A local anesthetic may be given before treatment to minimize pain and/or discomfort resulting from laser treatment. All other known risks will be disclosed to the subject via the informed consent process. Since this is an elective procedure and the subjects are volunteers, it can be assumed that their signature on the Informed Consent document indicates that the subject acknowledges and accepts the risks involved in the treatment of neck and chest rhytides.

**Safety Analysis:**

The potential events that are anticipated post treatment include prolonged erythema, discomfort, and herpes simplex reactivation. Other, less frequent transient potential events associated with any dermatological laser treatment include bleeding, crusting, numbness, itching, blistering and dryness. The occurrence of these events will be considered a treatment response and not an adverse device effect. Anticipated adverse device effects associated with any dermatological laser treatment include scarring, undesirable textural changes and depigmentation.

Grading of these clinical observations will be captured on the case report form under the following scale at each treatment visit and follow up visit:

0=none

1=trace

2=mild

3=moderate

4=severe

**Complications:**

If an unanticipated adverse event occurs at any time during or after the use of the laser within the study period, the Investigator must report it to the sponsor. The sponsor and the Institutional Review Board are to be notified within five days.

Any serious adverse event or complication directly attributable to the use of the laser system will be reported to Union Square Laser Dermatology, as soon as possible within twenty-four (24) hours or sooner and to the Institutional Review Board within five (5) days.

Any deaths, whether or not related to the use of the laser, will also be reported to Union Square Laser Dermatology, within twenty-four (24) hours or sooner and to the Institutional Review Board within five (5) days.

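### The 24-hour report of non-fatal serious adverse events is limited to those directly attributable to the laser, although the trial assesses the safety of laser plus cysteamine

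*Protocol*

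**What the plan says.** The Complications section of the Protocol has three reporting rules.

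- Unanticipated events. The rule opens "If an unanticipated adverse event occurs at any time during or after the use of the laser within the study period". The investigator reports to the sponsor, and the sponsor and the IRB are to be notified within five days. There is no test of cause.
- Serious events. The rule covers "Any serious adverse event or complication directly attributable to the use of the laser system", to be reported to the site organisation with the timing "as soon as possible within twenty-four (24) hours or sooner and to the Institutional Review Board within five (5) days".
- Deaths. "Any deaths, whether or not related to the use of the laser, will also be reported", on the same two time limits.

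Other sections describe what the trial is meant to assess. The Protocol Summary gives the purpose as efficacy and safety of the laser combined with the cream. Study population has every subject using the cream once a day at home, with the laser applied to one randomly chosen side. Risks and Discomforts gives the cream its own hazards: "Risks of the topical include temporary irritation, burning or heating up sensation".

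**The concern.** The treatment under study has two components, but the fast reporting route for serious events depends on attribution to one of them. On the lasered side cream and laser act on the same skin, so whether an event is directly attributable to the laser may be impossible to settle within 24 hours. A rule that needs that answer first leaves a serious event of unclear cause outside the fast route just when its cause is most in doubt.

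What is at stake is how soon the site organisation, the sponsor and the IRB learn of a serious event. No efficacy estimate or comparison is affected.

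**Working it through.** The Protocol states no figure on this point, so there is nothing to recompute. The check is to take each kind of serious event and see which rule in the Complications section applies.

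| Event in the study period | 24-hour report | Notice to IRB |
|---|---|---|
| Death, any cause | Yes | Within five days |
| Non-fatal serious, directly attributable to the laser | Yes | Within five days |
| Non-fatal serious, attributed to cysteamine, to both components or of unclear cause; unanticipated | No | Within five days (sponsor also) |
| The same, but of an anticipated type | No | No deadline stated |

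The steps behind the table are these.

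1. **Attribution limits the serious-event rule.** The rule for deaths sets causality aside in so many words ("Any deaths, whether or not related to the use of the laser"), and the sentence before it requires attribution. Read together, the contrast looks deliberate.

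2. **The unanticipated-event rule covers the third row.** Its condition is one of timing, "If an unanticipated adverse event occurs at any time during or after the use of the laser". At Visit 1 the cream is supplied and the first laser treatment is given, so the period after laser use spans essentially all cream exposure. The condition excludes little.

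3. **The fourth row is not empty.** The Safety Analysis section names prolonged erythema, discomfort and herpes simplex reactivation as anticipated. It adds less frequent events, blistering among them, and classes all of these as a response to treatment rather than an adverse device effect. Suppose a serious case of blistering or herpes reactivation is regarded as anticipated and is not firmly attributed to the laser. It then meets neither the serious-event rule nor the unanticipated-event rule. This assumes that anticipated is judged by type of event; the Complications section does not say how it is to be judged.

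4. **No other section supplies a deadline.** Study Oversight has a physician monitoring all adverse and serious adverse events, but names no recipient and no time limit.

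**The case against.** The strongest case on the other side is that little is left uncovered, and much of that case stands.

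- Deaths of any cause go out within 24 hours. This stands, and it confines the point to non-fatal events.
- Unanticipated events of any cause reach the sponsor and the IRB within five days, the same IRB deadline as for laser-attributable serious events. This stands; for these events only the 24-hour step is missing.
- The cream's listed risks are brief and mild, so a serious reaction to it would almost certainly count as unanticipated. This largely stands. The case with no deadline at all is mainly a serious event of a type listed under Safety Analysis whose cause is disputed.
- Grammatically, the attribution phrase could attach to the word complication alone, which would put every serious adverse event under the 24-hour rule. This is the less natural reading beside the rule for deaths. If it is what was meant, the sentence is ambiguous and still needs rewording.

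A reader might also infer that signals from the cream are lost, that the safety record is biased, or that the investigator would not see such events when deciding whether to stop the study. The Protocol does not support this. The Complications section governs notification, not data capture. The safety endpoint counts adverse events over treatment and follow-up without an attribution test. The text closing the Mottled Hyperpigmentation section commits to reporting any adverse effect in the results. Side effects are assessed at Visits 2, 3 and 4, and Study Oversight has all serious events monitored by a physician. The investigator is also the one who reports under the unanticipated-event rule, so the attribution condition does not decide what the investigator sees.

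**Conclusion.** The point holds within limits. As written, a non-fatal serious adverse event that is not directly attributed to the laser has no 24-hour report, and if it is of an anticipated type the Complications section gives it no deadline at all. That does not fit a trial whose stated purpose includes the safety of laser and cysteamine together.

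The consequence is delayed or absent expedited notice. The Protocol gives no event rate, so the expected number cannot be calculated; with 20 subjects planned, up to 25 allowed, a topical cream and a low-powered laser, it is likely to be small. The conclusion rests on reading the attribution phrase as limiting serious adverse events as well as complications. The no-deadline case also rests on judging anticipated by type of event. The wording should be corrected because it concerns subject safety and the change is cheap.

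**What to change.** In the Complications section, remove the laser-attribution condition from the serious-event sentence, so that every serious adverse event in the study period is reported within 24 hours whatever its cause, as deaths already are. Extend the existing five-day IRB notice at least to serious events possibly related to the laser, the cysteamine or both. Record relatedness as a separate case report form field with the options laser, cysteamine, both, neither and unclear, so that attribution is documented without deciding whether a 24-hour report is made.

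The cost is a reworded sentence, one added field and slightly more reporting.
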